10.2. Populations for Analysis

For the purposes of analysis, the following populations are defined:

- The Safety Population will include all participants who receive at least 1 injection of EN3835 or placebo. All safety and immunogenicity analyses will be based on the Safety Population.
- The ITT Population will include all randomized participants. Treatment group assignment will be based on the randomized treatment. The ITT population will be used for analysis of the primary and secondary endpoints.
- The FAS Population will include all ITT participants who receive at least 1 injection of EN3835 or placebo and have at least 1 post injection FFI pain subscale measures. Treatment group assignment will be based on the randomized treatment. This population will be used for analysis of the primary and secondary endpoints.
- The mITT Population will include all ITT participants who receive at least 1 injection of EN3835 or placebo and have both baseline and at least 1 post injection FFI pain subscale measures. The treatment group assignment will be based on the randomized treatment. This population will be used for analysis of the primary, secondary, and exploratory endpoints.

10.3. Statistical Hypotheses and Analyses

This section provides a general summary of the statistical methods to be used in analyzing study data. A more detailed statistical analysis plan (SAP) will be developed and finalized prior to database lock.

10.3.1. Efficacy Analysis

The ITT population will be the primary population for the efficacy analysis. Efficacy analyses will also be performed for the FAS and mITT populations as supportive analyses.

For the data collected at nodule level, the analyses will be performed at participant level and nodule level. The data interpretation will be based on participant level results. The nodule level results will be supportive. The details of how to map the data from nodule level to participant level will be specified in the SAP.

10.3.1.1. Primary Analysis

10.3.1.1.1. Primary Estimand

Primary Endpoint:

The difference between EN3835 and placebo in the mean change from Baseline (Day 1) to Day 57 on the foot pain subscale (total score on 9 items) of the FFI ranging from 0 (“None”) to 4 (“Extreme”).

The primary estimand is defined as follows:

In participants with plantar fibromatosis, what is the difference in mean change from baseline (Day 1) to Day 57 in foot pain score (as measured with the FFI pain subscale) between EN3835 and placebo regardless of discontinuation of study intervention?

The primary estimand includes the following components:

- Treatment of interest: The randomized study intervention (EN3835 or placebo)
- **Target Population:** Adult participants with plantar fibromatosis who are included in the ITT Population.
- **Variable (Endpoint) of interest:** Change from Baseline (Day 1) to Day 57 in FFI pain subscale score.
- **Treatments being compared:** The mean change from Baseline (Day 1) to Day 57 in FFI pain subscale score will be compared between EN3835 and placebo.
- **Intercurrent Event:** The treatment policy strategy will be adopted for primary analysis.
 - Any new or change in concomitant treatment will not be adjusted for in the primary analysis.
 - Early discontinuation from the study or loss to follow up: If participants do not have a FFI pain subscale score at Day 57, the missing values will be imputed before the analysis using a multiple imputation washout model. In multiple imputation washout model, all participants who are randomized and have a baseline assessment will be considered.
- **Population Level-Summary measure:** Least square mean (LSM) estimates for treatment difference between EN3835 and placebo.

10.3.1.1.2. Method of Analysis

The primary estimand will be based on the data at Baseline and Day 57. Therefore participants who discontinue study intervention or discontinue from the study will be encouraged to complete the remaining study visits and evaluations, and provide any additional follow-up information as required by the study. In cases where the participants do not have an FFI pain subscale score at Day 57 due to early study discontinuation, the missing values will be imputed before the analysis using a multiple imputation washout model. The details of the model will be specified in the SAP.

After imputation, the changes from Baseline to Day 57 will be analyzed using an ANCOVA model with treatment group as fixed effect, FFI pain subscale at baseline, the nodule size and the number of nodules as covariates. The summary measure, least squares (LS) mean estimate for treatment difference between EN3835 and placebo and their corresponding 95% confidence intervals (CIs) will be reported.

A sensitivity analysis with tipping-point approach will be implemented, the details of this approach will be specified in the SAP. In addition, another sensitivity analysis will be performed based all observed data up to Day 57. The changes from Baseline will be analyzed using a mixed

effect model for repeated measures (MMRM). This MMRM model will include treatment group, study visit, treatment by visit interaction as fixed effects, and the covariates of the baseline score, nodule size and the number of nodules. The repeated measure is the participant visits. The dependent variable will be the change from the Baseline at each visit. The summary measure, LSM estimate for treatment difference at Day 57 between EN3835 and placebo and their corresponding 95% CIs will be reported.

The FFI pain subscales, and their changes from Baseline will be summarized by study visit (if applicable) and treatment group using appropriate descriptive statistics.

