10. STATISTICAL CONSIDERATIONS AND METHODS

10.1. Sample Size Determination

The primary endpoint is the difference between EN3835 and placebo in the mean change from Baseline (Day 1) to Day 57 on the foot pain subscale (total score on 9 items) of the FFI ranging from 0 ("None") to 4 ("Extreme").

The sample size was estimated based on an interim analysis of the Day 57 data from Study EN3835-105, a dose-finding Phase 1 study. Assuming a difference in the mean change from Baseline to Day 57 in the pain subscale of FFI between EN3835 and placebo of 5.0 with a 10 standard deviation and 85% statistical power using a 2-sided test ($\alpha = 0.05$), 73 participants per treatment group (146 in total) will be needed to detect this difference between the 2 treatment groups. Assuming a dropout rate of 15%, the total sample size will be 172, eighty-six per treatment group for the study.

Participants will be screened to ensure that approximately 172 participants are randomized into 2 treatment groups, an EN3835 group and a placebo group in a 1:1 ratio.

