10.3.1.2.4. Other Secondary Endpoints and Exploratory Endpoints

The other secondary endpoints and exploratory endpoints including the mean changes from Baseline (Day 1) to study visits (Days 15, 29, 43 and 57) for FFI- Pain and Difficulty combined score, FFI- pain subscale, FFI- difficulty subscale, and FFI-activity limitation subscale, FFI-composite score, Pain intensity NRS, nodule size, and hardness measurement will be analyzed using the MMRM method based on observed data. The LSM estimates for the treatment difference at each visit and their corresponding 95% CIs will be reported.

The PGIS (overall, pain, difficulty, and activity limitation subscales) scores at each study visit (Days 15, 29, 43, and 57) will be compared between treatment groups using a rank based

analysis. The Hodges-Lehmann estimator and its 95% CIs will be provided to represent the median difference/location shift between the treatment groups.

In addition, response rates for the PGIC for PF overall and each individual subscale, participant satisfaction with treatments, Clinician Global Impression of Change Scale, and nodule consistency will be compared between treatment groups using the Cochran-Mantel-Haenszel method. The responder definition for each assessment will be detailed in the SAP.

Psychometric properties of the FFI will be assessed under a separate SAP. A series of tests are proposed to validate the FFI in the plantar fibromatosis patient population. Upon completion of the analyses, an overall impression and conclusion regarding the psychometric properties of the FFI instrument will be made, based on the analysis results.

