7.6.3.4. Other Secondary Endpoints: FFI

7.6.3.4.1. Mean Change from Baseline to Days 15, 29, 43, and 57 on the Pain Subscale

The mean change from Baseline (Day 1) to Days 15, 29, 43, and 57 on the Total Pain Subscale Score of the FFI ranging from 0 (“None”) to 4 (“Extreme”) with EN3835 vs placebo and their treatment differences will be estimated using the similar statistical model based on observed data using MMRM for the mITT population (Section 7.6.1.3).

7.6.3.4.2. Mean Change from Baseline to Days 15, 29, 43 and 57 on the FFI – Pain and Difficulty Combined Score

The mean change from Baseline (Day 1) to Days 15, 29, 43, and 57 on the Total Combined (Pain and Difficulty) Subscale Score with EN3835 vs placebo and their treatment differences will be estimated using the similar statistical model based on observed data using MMRM for the mITT population (Section 7.6.1.3).

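### The protocol's MMRM holds one baseline-score slope across all four visits; adding baseline-by-visit costs 3 degrees of freedom and brings a small gain in precision and comparability

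*Protocol*

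**What the plan says.** **Primary model.** Protocol 10.3.1.1.2 fits an "ANCOVA model with treatment group as fixed effect, FFI pain subscale at baseline, the nodule size and the number of nodules as covariates" to the change at Day 57, after imputation. Because only Day 57 is modelled, each covariate slope is specific to Day 57.

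**MMRM.** The same section describes a repeated-measures sensitivity analysis on all observed data up to Day 57, with "treatment by visit interaction as fixed effects, and the covariates of the baseline score, nodule size and the number of nodules". Treatment is crossed with visit; the three covariates are not. Each therefore has one slope for all four visits.

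**Where MMRM is used.**
- Protocol 10.3.1.2.4: the continuous by-visit endpoints "will be analyzed using the MMRM method based on observed data". These are FFI pain, combined score and hardness (secondary), and FFI difficulty, activity limitation, composite score, pain NRS and nodule size (exploratory).
- SAP 7.6.3.4: by-visit FFI pain and combined score are "estimated using the similar statistical model based on observed data using MMRM for the mITT population".
- SAP 7.6.1.1 and 7.6.2: MMRM carries both the observed-data and the tipping-point sensitivity analyses of the primary endpoint. SAP 7.6.3.1 and 7.6.3.3.1 do the same for key secondary endpoints 1 and 3.

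**What can be seen of the SAP model.** The participant-level term list in SAP 7.6.1.3 is redacted. The nodule-level lists in SAP 7.6.3.3.2 (hardness) and 7.6.4.7.2 (size) are visible; both enter baseline as a main effect only.

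**The concern.** Participants must score at least half of the pain scale to enter (Protocol 6.1), so some regression to the mean is plausible. How strongly change depends on baseline need not be the same at Day 15 and Day 57, and a second treatment may be given at Day 29, midway through the repeated measures. A common slope then averages over visits and fits none of them exactly.

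Two things are at stake. By-visit contrasts lose a little precision. In addition, SAP 7.6.1.1 offers the MMRM analyses as a gauge of the impact of missing data, yet the Day 57 MMRM and ANCOVA contrasts would differ even with no data missing. SAP 7.6.2 judges robustness by the point at which significance is lost, so near that point a gap caused by the covariate model could be read as sensitivity to missing data.

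**Working it through.** **1. The plan's own figure.** Inputs from Protocol 10.1: a difference "of 5.0 with a 10 standard deviation and 85% statistical power using a 2-sided test", alpha 0.05. By the normal approximation, n = 2 × (1.960 + 1.036)² × 10² / 5² = 71.8, so 72 per arm. The two-sample t calculation gives 73 (power 0.851; 72 gives 0.846), matching "73 participants per treatment group (146 in total) will be needed to detect this difference". Inflation: 146 / 0.85 = 171.8, so 172, or 86 per arm. The figure is reproduced, and the model change does not alter it.

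**2. Parameter count, four post-baseline visits.**

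| Mean model | Parameters |
|---|---|
| Protocol: intercept 1, treatment 1, visit 3, treatment × visit 3, three covariates 3 | 11 |
| Plus baseline × visit (4 − 1 = 3) | 14 |
| Plus size × visit and number × visit (3 + 3) | 20 |

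**3. Size by formula.** Let g be the gap between the Day 57 slope and the common slope, and s the baseline SD. Baseline variation left in the Day 57 residual raises its variance by g²s²/100 (residual SD 10). The estimate shifts by g times the chance difference in baseline means, which has SD g × s × √(2/73). Neither g nor s is in the documents. The entry floor confines the normalised score to 18–36, and a uniform spread over that range has SD 18/√12 = 5.2, so s = 3 to 6 is a reasonable range.

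| s | g | Variance increase | SD of shift (points) | Power at 73 per arm (0.856 if g = 0; normal approximation) |
|---|---|---|---|---|
| 3 | 0.1 | 0.09% | 0.05 | 0.855 |
| 4.5 | 0.3 | 1.82% | 0.22 | 0.849 |
| 4.5 | 0.5 | 5.06% | 0.37 | 0.838 |
| 6 | 0.5 | 9.00% | 0.50 | 0.825 |

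The power column shows what a test based on the common-slope MMRM would lose; the primary test is the ANCOVA.

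**4. Simulation with all three covariates.** Complete data, 73 per arm, baseline SD 4.5, unstructured covariance, true Day 57 difference −5. Slopes are assumed. The gap is the root-mean-square difference from the Day 57 ANCOVA estimate, in points.

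| Slopes, Day 15 to Day 57 | Gap, common slope | Gap, baseline × visit | Gap, all covariates × visit | Mean SE, common vs baseline × visit |
|---|---|---|---|---|
| −0.3 throughout | 0.16 | 0.13 | 0.00 | 1.620 vs 1.620 |
| −0.2 to −0.5 | 0.19 | 0.14 | 0.00 | 1.601 vs 1.597 |
| −0.1 to −0.7 | 0.25 | 0.13 | 0.00 | 1.565 vs 1.551 |

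The SE penalties are 0%, 0.3% (1.601/1.597) and 0.9% (1.565/1.551). Mean common-slope estimates were −5.08, −5.13 and −4.92. With 86 per arm and 15% dropout at random they ranged from −4.95 to −5.04, so bias is negligible. In those dropout runs the gap to an ANCOVA on observed Day 57 data was 0.35 to 0.41 with a common slope and still 0.29 to 0.32 with all covariates crossed with visit.

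**5. Simulation with baseline as the only covariate.** Complete data, 86 per arm, residual SD 10, within-person correlation 0.6, baseline SD 4.5 to 5.2. From near-constant slopes up to a steep set (−0.1 at Day 15 to −0.9 at Day 57), the common-slope SE is about 0 to 2.4% larger and the mean absolute gap at Day 57 is 0.04 to 0.25 points. The upper end is 0.25/5.0 = 5% of the design difference. The 95% confidence half-width is about 1.96 × 1.55 = 3.0 points.

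**The case against.** A common baseline slope is a legitimate pre-specified model. Under "an EN3835 group and a placebo group in a 1:1 ratio" it leaves the treatment contrast essentially unbiased. Several stronger readings are tempting, and the documents do not support them.

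- **That MMRM is the analysis for every by-visit secondary endpoint.** By-visit Clinician Global Impression of Change is also secondary and uses Cochran-Mantel-Haenszel (Protocol 10.3.1.2.4, SAP 7.6.3.5.1). Three of the four use MMRM, and their Day 57 contrasts also have an ANCOVA as primary or key secondary endpoints. MMRM stands alone for Days 15 to 43 and for the exploratory endpoints; these lie outside the testing hierarchy and carry nominal p-values.
- **That three degrees of freedom make the MMRM reproduce the ANCOVA.** Nodule size and number of nodules keep common slopes, so exact agreement in complete data needs nine. With dropout, an observed-data MMRM and an ANCOVA after washout imputation differ by design.
- **That the SAP's participant-level model lacks the term.** Protocol 10.3 calls itself a general summary, and the SAP 7.6.1.3 list is redacted. The term may already be there.
- **That early visits are over-adjusted and Day 57 under-adjusted.** This presumes a direction of slope change that the documents do not give.

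All four limits stand. What survives is that the readable protocol model and both readable nodule-level models omit a standard term, in a model with many uses.

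**Conclusion.** The point holds as a minor refinement. As written in the protocol, the MMRM adjusts for baseline differently from the Day 57 ANCOVA, and no reason is given. If slopes differ by visit, the cost is about 0 to 2.4% in the standard error and 0.04 to 0.25 points on average at Day 57; if they are constant, there is no loss of precision. These figures rest on assumed slopes, a baseline SD of 4.5 to 5.2, a residual SD of 10 and complete data. A baseline SD of 6 with a slope gap of 0.5 would raise the residual variance by 9%.

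A reader might infer that the primary result is at risk. It is not: the primary ANCOVA, its type I error and the sample size do not depend on this model, and the common-slope estimate showed no material bias. The benefit of the change is slightly tighter by-visit contrasts and the removal of one avoidable difference between the primary and its sensitivity analyses.

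**What to change.** Before the SAP is finalised:

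1. Add baseline-score-by-visit to the MMRM fixed effects in Protocol 10.3.1.1.2.
2. Add the corresponding baseline-by-visit term to the nodule-level models in SAP 7.6.3.3.2 and 7.6.4.7.2.
3. Confirm that the redacted term list in SAP 7.6.1.3, to which the other MMRM sections refer, contains the same term. If it already does, only the protocol and the nodule-level models need aligning.
4. Optionally, add nodule-size-by-visit and number-of-nodules-by-visit to the participant-level model if the Day 57 MMRM contrast is meant to match the ANCOVA's covariate adjustment in complete data.

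The cost is 3 extra parameters, or 9 with the optional terms, with about 172 participants. No new data are needed and the sample size does not change.

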10.3.1.2. Secondary and Exploratory Analysis

All secondary and exploratory endpoints will be summarized by study visit (if applicable) and treatment group using appropriate descriptive statistics.

10.3.1.2.1. Key Secondary Endpoint 1

Key Secondary Endpoint 1:

The difference of mean change from baseline to Day 57 for FFI Pain and Difficulty combined score between EN3835 and placebo

Key Secondary Estimand 1: In participants with plantar fibromatosis, what is the difference in mean change from baseline to Day 57 in foot pain and difficulty combined score (as measured with combined score of the FFI pain subscale and the FFI difficulty subscale) between EN3835 and placebo, regardless of discontinuation of study intervention?

The key secondary estimand 1 includes the following components:

- Treatment of interest: The randomized study treatment (EN3835 or placebo)
- **Target Population:** Adult participants with plantar fibromatosis who are included in the ITT Population.
- **Variable (Endpoint) of interest:** Change from Baseline (Day 1) to Day 57 in FFI pain and difficulty combined score.
- **Treatments being compared:** The mean change from Baseline (Day 1) to Day 57 FFI pain and difficulty combined score will be compared between EN3835 and placebo.
- **Intercurrent Event:** The treatment policy strategy will be adopted for primary analysis.
 - Any new or change in concomitant treatment will not be adjusted for primary analysis.
 - Early discontinuation from the study or loss to follow up: If participants do not have FFI pain and difficulty combined score at Day 57, the missing values will be imputed before the analysis using a multiple imputation washout model. In multiple imputation washout model, all participants who are randomized and have a baseline assessment will be considered.

- **Population Level-Summary measure:** LSM estimate for treatment difference between EN3835 and placebo.

The method of analysis (including sensitivity analysis) for key secondary endpoint #1 will follow the same method of analysis for primary endpoint.

10.3.1.2.2. Key Secondary Endpoint 2

Key Secondary Endpoint 2: The difference in the proportion of participants treated with EN3835 or placebo reporting “Minimally Improved” (+1), “Much Improved” (+2), or “Very Much Improved” (+3) on the Clinician Global Impression of Change Scale at Day 57.

Key Secondary Estimand 2: In participants with plantar fibromatosis, what is the difference in the proportion of participants with an improvement (as assessed by the investigators with rating of “Minimally Improved” (+1), “Much Improved” (+2), or “Very Much Improved” (+3) on the Clinician Global Impression of Change Scale) between EN3835 and placebo at Day 57, regardless of study withdrawal?

The key secondary estimand 2: includes the following components:

- Treatment of interest: The randomized study treatment (EN3835 or placebo)
- **Target Population:** Adult participants with plantar fibromatosis who are included in the ITT Population.
- **Variable (Endpoint) of interest:** Difference in the proportion of Clinician Global Impression of Change (CGIC), a 7-point scale ranging from –3 (“Very Much Worse”) to +3 (“Very Much Improvement”) at Day 57.
- **Treatments being compared:** The difference in proportion at Day 57 in CGIC will be compared between EN3835 and placebo.
- **Intercurrent Event:** The treatment policy strategy will be adopted for primary analysis.
 - Any new or change in concomitant treatment will not be adjusted for primary analysis.
 - Early discontinuation from the study or loss to follow up: All participants with early discontinuation or loss to follow up will be considered as non-responders. The responder is defined as a participant for whom the investigator reports a score to be “Minimal Improvement”, “Much Improvement” or “Very Much Improvement” on the Clinician Global Impression of Change Scale at Day 57.
- **Population Level-Summary measure:** The stratum adjusted risk difference, associated 95% CI and *p* value will be presented separately for each visit between EN3835 and placebo.

The proportions (response rates) will be compared between treatment groups using the Cochran-Mantel-Haenszel method.

A sensitivity analysis with tipping-point approach will be implemented for key secondary endpoint #2. The details of this approach will be specified in the SAP.

10.3.1.2.3. Key Secondary Endpoint 3

Key Secondary Endpoint 3: The difference of mean changes from Baseline to Day 57 for hardness measurements between EN3835 and placebo.

Key Secondary Estimand 3: In participants with plantar fibromatosis, what is the difference in mean change from baseline to Day 57 in hardness measurements (as measured by durometer) between EN3835 and placebo, regardless of discontinuation of study intervention?

The key secondary estimand 3: includes the following components:

- Treatment of interest: The randomized study treatment (EN3835 or placebo)
- **Target Population:** Adult participants with plantar fibromatosis who are included in the ITT Population.
- **Variable (Endpoint) of interest:** Mean change from Baseline (Day 1) to Day 57 in nodular hardness.
- **Treatments being compared:** The mean change from Baseline (Day 1) to Day 57 nodular hardness will be compared between EN3835 and placebo.
- **Intercurrent Event:** The treatment policy strategy will be adopted for primary analysis.
 - Any new or change in concomitant treatment will not be adjusted for primary analysis.
 - Early discontinuation from the study or loss to follow up. If participants do not have nodular hardness at Day 57, the missing values will be imputed before the analysis using a multiple imputation washout model. In multiple imputation washout model, all participants who are randomized and have a baseline assessment will be considered.
- **Population Level-Summary measure:** LSM estimate for treatment difference between EN3835 and placebo.

This estimand will be based on the data at Baseline and Day 57. The imputation and the analysis methods (including sensitivity analysis) are similar to the primary estimand. The summary measure, LSM estimates for treatment difference between EN3835 and placebo, and the corresponding 95% CIs will be reported.

